	
Table S2: Power estimates to reject the secondary null hypothesis
 

Antigen	Endpoint	Estimated response (%)*	Non-inferiority margin	Power (%)	

A	% \geq1:8	>99.9	10%	100	

C	% \geq1:8	>99.9	10%	100	

Y	% \geq1:8	97.8	10%	100	

W	% \geq1:8	97.8	10%	100	

Overall	100	

 
Note: Evaluable subjects: Group 1 = 261 subjects; Group 2 = 261 subjects *Estimated responses are based on results observed in MET39
	Antigen	Endpoint	Estimated response (%)*	Non-inferiority margin	Power (%)	A	% \geq 1:8	>99.9	10%	100	C	% \geq 1:8	>99.9	10%	100	Y	% \geq 1:8	97.8	10%	100	W	% \geq 1:8	97.8	10%	100	Overall				100
Antigen	Endpoint	Estimated response (%)*	Non-inferiority margin	Power (%)																											
A	% \geq 1:8	>99.9	10%	100																											
C	% \geq 1:8	>99.9	10%	100																											
Y	% \geq 1:8	97.8	10%	100																											
W	% \geq 1:8	97.8	10%	100																											
Overall				100																											

Table of Study Procedures – Group 1 and Group 2

Phase III Study, 4 Visits, 2 Vaccinations visits, 3 Blood Samples, 4 Telephone Calls and 12 Months Duration per Subject

Visit (V) / Contact	Visit 1	Telephone Call (TC) 1*	Visit 2	TC 2†	Visit 3	TC 3*	Visit 4	TC 4 Follow-up contact‡
Approximate age of subjects	6 to 7 months§		7 to 8 months	11.5 to 12.5 months	12 to 13 months		13 to 14 months	18 to 19 months
Study timelines (days)	D0	Visit 1 +8 days	Visit 1 +30 days	Visit 3 -14 days	≥6 months post-Visit 1	Visit 3 +8 days	Visit 3 +30 days	Visit 3 +180 days
Time windows (days)		+2 days	+21 days			+2 days	+21 days	+30 days
Informed consent	X							
Inclusion/exclusion criteria	X							
Collection of demographic data	X							
Medical history	X							
Physical examination (including temperature measurement) **	X				X			
Contact interactive response technology (IRT) system for randomization/allocation of subject number/vaccine group assignment	X							
Review of temporary contraindications for blood sampling††	X		X		X		X	
Blood sampling (BL) (3 mL)	BL0001‡‡		BL0002A§§		BL0002B‡‡***		BL0003	
Review of warning and precautions to vaccinations	X				X			

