§§§§The memory aid will be used only for the recording of SAEs (including AESIs) and MAAEs from Visit 4 to the 6-month follow-up phone call (TC4).

Table of Study Procedures – Group 3 and Group 4

Phase III Study, 3 Visits, 2 Vaccination visits, 2 Blood Samples, 10-month Duration per Subject

Visit / Contact	Visit 1	TC 1*	Visit 2	TC 2*	Visit 3	TC 3 Follow-up contact†
Approximate age of subjects	17 to 19 months		20 to 23 months		21 to 24 months	27 to 30 months
Study timelines (days)	D0	Visit 1 +8 days	≥3 months post-Visit 1	Visit 2 +8 days	Visit 2 +30 days	Visit 2 +180 days
Time windows (days)		+2 days		+2 days	+21 days	+30 days
Informed consent	X					
Inclusion/exclusion criteria	X					
Collection of demographic data	X					
Medical history	X					
Physical examination (including temperature)‡	X					
Randomization/allocation of subject number	X					
Review of temporary contraindications for blood sampling§	X				X	
Blood sampling (BL) (3 mL)	BL0001**				BL0002	
Review of warning and precautions to vaccinations	X		X			
Review of contraindications to subsequent vaccinations and conditions for withdrawal††			X			
Contact IRT system for vaccine assignment	X		X			
Vaccination with MenACYW conjugate vaccine or MenaCTra®	X		X			
Immediate surveillance (30 minutes)	X		X			
Diary card provided	DC1		DC2			
Telephone Call		X		X		X
Diary card reviewed and collected			DC1		DC2	
Recording of solicited injection site and systemic reactions‡‡	X		X			
Recording of unsolicited adverse events		Recorded from D0 to D30 after each vaccination visit				
Reporting of SAEs (including AESIs) and MAAEs§§		To be reported throughout the study period				
Collection of reportable concomitant medications	X		X		X	
MA provided					X	
Completion at End of study					X	

*This call will be made 8 days after the respective vaccinations. If day 8 falls on a weekend or holiday, the telephone call may be made on the following business day. During this telephone call, the staff will find out whether the subject experienced any SAE and/or MAAE not yet reported, and will remind the subject's parent / guardian to continue using the diary card, to bring the diary card to the study center at the next visit, and to confirm the date and time of the next visit.

†Staff will contact the subject's parent / guardian by telephone at 6 months (+ 30 days) after the last vaccination visit to identify the occurrence of any SAEs (including any AESIs) and MAAEs not yet reported.

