5.1 Description of the Overall Study Design and Plan

5.1.1 Study Design

This is a Phase III, randomized, parallel group, active-controlled, multi-center study to compare the immunogenicity and describe the safety of MenACYW conjugate vaccine and MENVEO® when administered in a 1 + 1 schedule and concomitantly with routine pediatric vaccines in healthy infants and toddlers in the US. This study will also describe the safety and immunogenicity of MenACYW conjugate vaccine and Menactra® when administered in a 1 + 1 schedule to healthy toddlers in the US. For each age group at enrollment, the study will have a modified double-blind design, i.e., modified double-blind between Group 1 and Group 2, and between Group 3 and Group 4.

Approximately 1070 subjects will be enrolled. Approximately 870 healthy infants 6 to 7 months of age will be randomized 1:1 to 2 groups, and 200 healthy toddlers 17 to 19 months of age will be randomized 1:1 to 2 groups:

- **Group 1:** MenACYW conjugate vaccine + routine pediatric vaccines at 6 to 7 months of age and 12 to 13 months of age
- **Group 2:** MENVEO® + routine pediatric vaccines at 6 to 7 months of age and 12 to 13 months of age
- **Group 3:** MenACYW conjugate vaccine at 17 to 19 months of age and 20 to 23 months of age
- **Group 4:** Menactra® at 17 to 19 months of age and 20 to 23 months of age

The vaccination schedule and blood sampling is further detailed in [Table 5.1](#) and [Table 5.2](#).

All subjects in Group 1 and Group 2 will receive a dose of either MenACYW conjugate vaccine or MENVEO® with the following routine pediatric vaccines to ensure compliance with the Advisory Committee on Immunization Practices (ACIP) recommendations:

- Diphtheria, tetanus and acellular pertussis (DTaP) at 6 months of age
- Inactivated poliovirus (IPV) at 6 months of age
- *Haemophilus influenzae* type b (Hib) at 6 months of age. In children immunized with PedvaxHIB® at 2 and 4 months of age, a third dose of Hib vaccine at 6 months of age is not required.
- Pneumococcal 13-valent conjugate (Prevnar 13®, PCV13) at 6 and 13 months of age
- Rotavirus (RotaTeq®) at 6 months of age

- Hepatitis B at 6 months of age
- Measles, mumps, and rubella (M-M-R®II) at 12 months of age
- Varicella (Varivax®) at 12 months of age.

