Note: If Day 8 falls on a weekend or a holiday, the telephone call may be made on the following business day.

- 1) Record relevant information concerning the subject's health status on the telephone contact form. If an SAE (including AESI) occurred, follow the instructions in [Section 10](#) for reporting it.
- 2) Remind the parent / guardian to do the following:
 - Complete the D0 to D07 pages of the diary card.
 - Complete the remaining pages of the diary card, and bring them to the next visit.
 - Notify the site in case of an SAE.

Visit 2 (30 [+21] days after Visit 1): Collection of Safety Information and Blood Sample

- 1) Collect and review the diary card (DC1) with the parent / guardian, including any AEs, medications, or therapy that occurred since vaccination. If an SAE, including an AESI, has occurred, follow the instructions in [Section 10](#) for reporting it.
- 2) For subjects providing a blood sample at Visit 2 (50% of the subjects enrolled in Group 1 and Group 2):
 - Review temporary contraindications for blood sampling. Ensure the subject has not had any antibiotics within the previous 72 hours (3 days).
 - Collect 3 mL of blood (BL0002A) (see [Section 7](#) for detailed instructions regarding the handling of blood samples).
- 3) Give the parent / guardian a diary card (DC2).
- 4) Remind the parent / guardian to expect a telephone call within 14 days before Visit 3 and to bring back the diary card when they return for Visit 3 at a specified date and time.
- 5) Remind the parent / guardian to notify the site in case of an SAE.
- 6) Complete the relevant CRFs for this visit.

Telephone Call 2 (within 14 days before Visit 3, at 11.5 to 12.5 months of age)

- 1) Contact the subjects' parent/ guardian by telephone within 14 days before Visit 3 to remind them about the forthcoming study visit.
- 2) If the subject will not continue in the study:

- Review the diary card. Ask the subject's parent / guardian if the subject has experienced any SAE and / or MAAE in the time since vaccination that has not been reported to the study personnel. If an SAE, including an AESI, has occurred, follow the instructions in [Section 10](#) for reporting it.
- Request the subject's parent / guardian to mail the diary card to the site.

Visit 3 (6 months after Visit 1 [subjects must be 12 to 13 months of age]): Collection of Safety Information, Blood Sampling, and Vaccination

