- 13) Give the parent / guardian a diary card (DC1), a thermometer, and a ruler, and go over the instructions for their use. Instruct the parent / guardian to retain the thermometer and ruler throughout the duration of the study. At each subsequent visit, confirm that the parent /guardian has retained the thermometer and ruler, replace only as necessary.
- 14) Remind the parent / guardian to expect a telephone call 8 days after Visit 1 and to bring back the diary card when they return for Visit 2 at a specified date and time.
- 15) Remind the parent / guardian to notify the site in case of an SAE.
- 16) Complete the relevant CRFs for this visit.

Telephone Call 1 (8 days [+2 days] after Visit 1)

Note: If Day 8 falls on a weekend or a holiday, the telephone call may be made on the following business day.

- 1) Record relevant information concerning the subject's health status on the telephone contact form. If an SAE (including AESI) occurred, follow the instructions in [Section 10](#) for reporting it.
- 2) Remind the parent / guardian to do the following:
 - Complete the D0 to D07 pages of the diary card.
 - Complete the remaining pages of the diary card, and bring them to the next visit.
 - Notify the site in case of an SAE.

Visit 2 (3 months after Visit 1 [at 20 to 23 months of age]): Collection of Safety Information and Vaccination

- 1) Review the diary card (DC1) with the parent / guardian, including any AEs, medications, or therapy that occurred since vaccination. If an SAE, including an AESI, has occurred, follow the instructions in [Section 10](#) for reporting it.
- 2) Perform a physical examination, including, but not limited to, examination of the head (ear, nose, and throat), neck, heart, lungs, abdomen, and extremities. If a routine examination had been performed within the past week by a qualified health care provider, it does not need to be repeated unless there were changes in health status, in which case it may be limited to the affected area.
- 3) Measure temperature. If the temperature is $\geq 38^{\circ}\text{C}$ ($\geq 100.4^{\circ}\text{F}$), postpone vaccination until the condition is resolved.
- 4) Review warnings and precautions to vaccinations.
- 5) Review contraindications for subsequent vaccinations and conditions for withdrawal
- 6) Contact IRT system for vaccine assignment.
- 7) Administer the study vaccines. The vaccine should be administered in the assigned location (see Operating Guidelines) and documented appropriately:

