12.2.3.2 Per-Protocol Analysis Set 2 (PPAS2)

During the second year of life, the immunogenicity analyses for various antigens will be performed on serology obtained 30 days after the given antigen administration if blood collection is planned at that time.

PPAS2 will be a subset of FAS2. The subjects presenting with at least one of the following relevant protocol deviations will be excluded from the PPAS2:

- Subject did not meet all protocol-specified inclusion criteria or met at least one of the protocol-specified exclusion criteria
- Subject did not complete the vaccination schedule including the infant and the second year of the study:
 - Group 1 and Group 2: Up to 12-13 month vaccinations, including the infant schedule
 - Group 3 and Group 4: Up to 23 month vaccinations
- Subject received a vaccine other than the one that he / she was randomized to receive
- Preparation and / or administration of vaccine was not done as per-protocol
- Subject did not receive vaccine in the proper time window
 - Group 1 and Group 2
 - Visit 3: 12 to 13 months of age
 - Group 3 and Group 4
 - Visit 1: 17 to 19 months of age
 - Visit 2: 20 to 23 months of age
- Subject did not provide a post-dose serology sample in the proper time window or a post-dose serology sample was not drawn

- Group 1 and Group 2
 - Blood Sampling 0003: Visit 4 (Visit 3 + 30 days [± 21 days])
- Group 3 and Group 4
 - Blood Sampling 0002: Visit 3 (Visit 2 + 30 days [± 21 days])
- Subject received a protocol-prohibited therapy / medication / vaccine (reportable concomitant medication of category 2 and / or category 3)
- Subject had other protocol violations that affected the subject's immune response, as determined by the clinical team before locking the database

In addition to the reasons listed above, subjects will also be excluded from the PPAS if their serology sample did not produce a valid test result (i.e., results for all antigens are missing).

Vaccine correctness required by the PPAS2 includes not only the 2 doses of MenACYW conjugate vaccine, MENVEO[®], or Menactra[®] but also, for subjects in groups 1 and 2, the concomitant vaccines (MMR, Varicella) as scheduled in the second year of life.

In the event of a local or national immunization program with a pandemic influenza vaccine, subjects who receive 1 or more doses of a pandemic influenza vaccine at any time during the study will not be withdrawn from the study.

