5.2.3.2 Per-Protocol Analysis Set 2 (PPAS2)

During the second year of life, the immunogenicity analyses for various antigens will be performed on serology obtained 30 days after the given antigen administration if blood collection is planned at that time.

PPAS2 will be a subset of FAS2. The subjects presenting with at least one of the following relevant protocol deviations will be excluded from the PPAS2:

- Subject did not meet all protocol-specified inclusion criteria or met at least one of the protocol-specified exclusion criteria
- Subject did not complete the vaccination schedule including the infant and the second year of the study:
 - Group 1 and Group 2: Up to 12-13 month vaccinations, including the infant schedule
 - Group 3 and Group 4: Up to 23 month vaccinations
- Subject received a vaccine other than the one that he / she was randomized to receive
- Preparation and / or administration of vaccine was not done as per-protocol
- Subject did not receive vaccine in the proper time window
 - Group 1 and Group 2
 - Visit 3: 12 to 13 months of age
 - Group 3 and Group 4
 - Visit 2: 20 to 23 months of age
- Subject did not provide a post-dose serology sample in the proper time window or a post-dose serology sample was not drawn
 - Group 1 and Group 2
 - Blood Sampling 0003: Visit 4 (Visit 3 + 30 days [± 21 days])
 - Group 3 and Group 4
 - Blood Sampling 0002: Visit 3 (Visit 2 + 30 days [± 21 days])

- Subject received a protocol-prohibited therapy / medication / vaccine (reportable concomitant medication of category 2 and / or category 3)
- Subject had other protocol violations that affected the subject's immune response, as determined by the clinical team before locking the database

In addition to the reasons listed above, subjects will also be excluded from the PPAS if their serology sample did not produce a valid test result (i.e., results for all antigens are missing).

Vaccine correctness required by the PPAS2 includes not only the 2 doses of MenACYW conjugate vaccine, MENVEO®, or Menactra® but also, for subjects in groups 1 and 2, the concomitant vaccines (MMR, Varicella) as scheduled in the second year of life.

In the event of a local or national immunization program with a pandemic influenza vaccine or coronavirus vaccine, subjects who receive 1 or more doses of a pandemic influenza vaccine or coronavirus vaccine at any time during the study will not be withdrawn from the study.

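### Does PPAS2 need its own rule on the minimum interval between the two meningococcal doses?

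*SAP*

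**What the plan says.** **Schedule.** The Table of Study Procedures puts the second dose in Groups 1 and 2 at "≥6 months post-Visit 1" and in Groups 3 and 4 at "≥3 months post-Visit 1". SAP Tables 3.3 and 3.4 repeat both. Protocol 5.1.4 gives interval and age together: "Visit 3 (6 months after Visit 1 [subjects must be 12 to 13 months of age" for the infants and "Visit 2 (3 months after Visit 1 [at 20 to 23 months of age" for the toddlers. The row for time windows is blank at both second-dose visits.

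**Analysis set.** The PPAS2 item on vaccination outside the proper window lists "Visit 3: 12 to 13 months of age" for Groups 1 and 2 and "Visit 2: 20 to 23 months of age" for Groups 3 and 4 (SAP 5.2.3.2). Protocol 12.2.3.2 has the same second-dose lines and adds "Visit 1: 17 to 19 months of age" for Groups 3 and 4. The SAP leaves that line out, and SAP 5.7 does not mention it. Neither list gives an interval.

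**Related rules.** PPAS2 also excludes children whose vaccine was not prepared or administered as the Protocol requires, and children with other violations that the clinical team judges, before lock, to have affected the immune response. Protocol 5.2.7.1 requires a postponed dose to stay within the timeframe in the Table of Study Procedures. Protocol 5.2.10 gives failure to keep to time windows as an example of significant non-compliance. Protocol 11.3 plans a blind data review before lock.

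**PPAS3.** SAP 5.2.3.3 requires the sample before dose 2 to be drawn at Visit 3 in its proper window, without restating that window.

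**The concern.** Two conditions are scheduled for the second dose, but the analysis-set item that deals with timing names one. Infants may enrol up to 224 days of age, and Protocol 5.1.1 lists "Measles, mumps, and rubella (M-M-R®II) at 12 months of age", so vaccination close to the first birthday is a natural case. A late enrolee vaccinated then meets the age line but misses the scheduled interval.

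A programmer working only from the time-window lines would keep that child. A colleague applying the administration item would remove the same child. If two competent teams can build different versions of PPAS2 from the same data, the population of the primary test is not fully fixed in advance, and the FAS2 analysis is only exploratory. In Groups 3 and 4 the age lines alone set almost no minimum interval. A Visit 3 sample taken well before six months could also enter the descriptive result for secondary objective 4.

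**Working it through.** **1. The plan's own figure.** Inputs from SAP 5.1.1.2 and 5.5: 261 evaluable per group (435 × 0.60 = 261), margin 10 points, one-sided 2.5%, equal true rates of 97.7% (A), 97.8% (C), 93.3% (Y) and 86.7% (W). Farrington-Manning power is

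Φ[(0.10 − 1.96 × SE₀) / SE₁],

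where SE₀ uses the rates fitted under a true difference of −10 points and SE₁ uses the assumed rates.

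For serogroup W:
- fitted rates 0.803 and 0.903, so SE₀ = 0.0307
- SE₁ = √(2 × 0.867 × 0.133 / 261) = 0.0297
- power = Φ(1.339) = 91.0%

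Y gives 99.0%, and A and C round to 100%. The product is 90.1%, against 90.0% stated. The figure reproduces, and the dose interval does not enter it.

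**2. What the age lines allow, Groups 1 and 2.** Take 12 months as 365 days and six months as 183 days.
- Shortest interval: 365 − 224 = 141 days (20.1 weeks), which is 183 − 141 = 42 days short.
- Longest interval at 12 months of age: 365 − 168 = 197 days, which meets the schedule.
- With dose 2 at 365 days, enrolment at 183 to 224 days falls short. That is 42 of the 57 eligible enrolment days.

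These are limits of one line of text, not a forecast: such a child must also have been vaccinated earlier than the schedule allows. For reference, Protocol 5.1.2 reports a 12-week minimum for a two-dose series started at 7 to 23 months.

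**3. Groups 3 and 4.** First dose on the day before 20 months and second dose at 20 months gives 1 day. Reaching it means ignoring the scheduled three months entirely. These groups serve a descriptive objective only.

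**4. Whether keeping such children could matter.** If a share f of each arm has a short interval, and the between-arm difference in those children departs by d from that in the rest, the PPAS2 difference moves by f × d. The documents give neither quantity. Assuming d = 10 points (a whole margin), the shift is 0.2 points at f = 2%, 0.5 at 5%, 1.0 at 10% and 2.0 at 20%. Nothing in the documents points to a d of that size or to its sign.

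**5. What an explicit exclusion would cost.** The loss is assumed, since no rate is given.

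| Loss from 261 per group | n per group | Overall power |
|---|---|---|
| 0% | 261 | 90.1% |
| 2% | 256 | 89.4% |
| 5% | 248 | 88.3% |
| 10% | 235 | 86.3% |
| 15% | 222 | 83.9% |
| 20% | 209 | 81.1% |

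With 30% non-evaluable (304 per group), power is 94.3%. A further 2% loss (298 per group) leaves 93.8%.

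**6. The two smaller points.** The missing Visit 1 age line removes nothing of substance: inclusion criterion 1 already fixes that age, and failing an inclusion criterion excludes a child from PPAS2. The PPAS3 sample is tied to Visit 3, whose age and interval are both in SAP Table 3.3.

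**The case for a change.** The best case for a change is that membership of the primary analysis set should follow from the SAP without judgement. PPAS2 has a dedicated timing item with explicit limits, and the interval is not among them. The administration item may be meant for handling and injection rather than timing, and the remaining item depends on the clinical team's view of the immune response. Adding the interval would take one line and one date difference, and excluded children with valid serology would stay in FAS2.

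Part of this stands. The time-window item gives no interval threshold, and a cross-reference to the procedure tables would remove the doubt.

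It does not show that the plan as written goes wrong. Protocol 5.2.7.1 and 5.2.10 make it an ordinary reading, not a strained one, that a dose given before its scheduled interval was not administered as the Protocol requires. The remaining judgement is exercised before lock under a planned blind review, so there is no evident way for it to favour an arm. An age-based set also matches the primary objective, which defines the regimen by age at each dose. The change is not quite free either: the Protocol has the same age-only second-dose lines, so the SAP would depart from it and need an entry in 5.7. If short intervals are rare, the rule changes almost nothing. If they are common, it removes more randomised children from a set already planned to lose up to 40%.

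**Conclusion.** No change is needed. The PPAS2 timing lines do not repeat an interval that stands in the procedure tables of both documents. It is a gap that analysts can fill sensibly from those tables, the administration item and the blind review before lock.

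The age lines alone would admit an interval as short as 141 days in Groups 1 and 2, but no count of such children is available and the schedule works against their occurring. The rule applies alike to both arms, no stated figure is in error, and no effect on the primary conclusion is shown. An added exclusion would take overall power from 90.1% to between 89.4% and 81.1% for assumed losses of 2% to 20%, in return for no demonstrated reduction in bias.

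This rests on three assumptions: sites largely keep to the scheduled interval, the review before lock is blind as planned, and the reading of the administration item is settled at that review for both arms alike. A cross-reference from the PPAS2 and PPAS3 timing items to the procedure tables, and a note in SAP 5.7 on the omitted Visit 1 line, would be tidy but would not alter a result. Which interval is clinically appropriate is not judged here.
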